6 STUDY INTERVENTION

6.1 STUDY INTERVENTION(S) ADMINISTRATION

6.1.1 STUDY INTERVENTION DESCRIPTION

The KiT intervention is a text messaging algorithm that will operate like a chatbot, querying adolescents with T1D about their confidence with different aspects of T1D self-management as they are preparing to transition to adult diabetes care. The KiT intervention has five components of messaging (see below); if enrolled in the intervention group, participants will receive all four types of messages while the control group will only receive messages pertaining to the fourth category:

- 1) Personalized Educational Content (referred to as “push content”): KiT will send some personalized educational content to participants based on self-reported confidence ratings as measured by the “Readiness of Emerging Adults with Diabetes Diagnosed in Youth” (READDY) tool and participants self-reported interest in particular topics. The KiT intervention will send a combination of young-adult friendly educational text messages and links to existing trusted online resources about topics such as driving and diabetes, alcohol and diabetes, managing diabetes-related stressors; and diabetes and sexual health and function.
 - a. With respect to managing stressors related to living with type 1 diabetes, KiT will initiate a series of support-based text-messages offering suggestions to improve behavioral health using suggested coping strategies. These behavioral health text messages will be created by an expert group that includes: a pediatric psychologist [name] who specializes in working with chronically medically ill children and youth and is a certified diabetes educator (CDE); a pediatric endocrinologist who specializes in diabetes [name]; and our study’s patient partner [name]
- 2) Standard Educational Curriculum: deliver messages and reminders related to transition to adult diabetes care that are relevant to all adolescents with T1D preparing to transition to adult care. These messages will support participants as they navigate adult diabetes care. Messages will cover topics such as preparing for an upcoming clinic appointment, reminders about booking appointments, refilling and paying for diabetes medication and supplies.
- 3) Provide participant compensation for filling out questionnaires about clinic attendance, information about diabetes care and self-management such as diabetes device use and measures of glycemia, and patient reported outcome measures (READDY, BDA Stigma subscale, and SEDM; all at baseline, 6 months and 12 months). All participants (in both the control and experimental groups), will be provided the same compensation at the same time-points once all outcome measures at each time-point (baseline, 6 months and 12 months) have

been completed: a \$20 Amazon gift-card for completion of outcome measures at each time-point for a maximum total value of \$60 in Amazon gift-cards per participant. This compensation amount was determined based on the total estimated time to complete all outcome measures (total of 4 outcome measures plus initial survey) at each time-point – approximately 15-20 minutes. This compensation amount per time-point is further justified as other similar studies in the same population offered \$20 for completion of 8-10 outcome measures that took approximately 45 minutes to complete. When KiT sends messages with links to the REDcap-based outcome measures, KiT will also remind participants that they will only receive an automatic e-gift card via KiT text-message once they complete all questionnaires at each time-point.

- 4) Question and Answer (Q&A) feature: participants in the intervention arm can message the KiT intervention with their T1D related questions and the intervention will send links (where available) via text-message, to relevant resources from the validated resources collected in the environmental scan.
- 5) LLM Chatbot feature: in addition to the Question and Answer (Q&A) feature, participants in the intervention arm can also access a LLM chatbot via a link KiT shares that is outside of the SMS-based intervention. Participants can ask the LLM chatbot their T1D related questions and the LLM chatbot will send answers in a natural language format and links (when available) from the same validated resources collected in the environmental scan. If no resource relevant to the question is found, a message stating this is presented to participants.

Personalized Educational Content: After considering over 20 available transition readiness tools and questionnaires used in the diabetes population, the KiT subcommittee (consisting of our patient partner, and four pediatric diabetes endocrinologists), selected the READDY tool as the preferred diabetes-transition tool to help guide the intervention topics list, content creation and messages. Alongside the KiT subcommittee, an environmental scan was conducted to find what online resources related to T1D transition were provided by organizations, hospitals, institutions and governmental groups across Canada. These resources were categorized based on relevance to T1D transition, availability in French and English, production quality, accessibility, web-site screen resolution adjusting on mobile device, and licensing. Furthermore, these resources were itemized as “topic areas” and mapped to the relevant domain of the READDY tool in an effort to distinguish which items on the READDY tool that the KiT intervention could provide education and resources on. Therefore, the results of the environmental scan that mapped to the READDY tool serves as the knowledge base for the KiT algorithm to deliver educational content and resources. The environmental scan included only Canadian sources, however, we may opt to include non-Canadian educational resources if they are deemed by the research team to be credible.

Also, during Phase 1 of the KiT study, we conducted one-on-one semi-structured interviews and co-design sessions in Ontario and Quebec with pediatric and young adult patients with T1D, as well as pediatric and young adult diabetes providers, asking to help design a digital tool for youth to keep in touch with their diabetes team during transition to adult care. The interviews and co-design sessions revealed what topics, gaps and challenges patients and providers felt were important to address with youth transitioning to adult diabetes care. The most salient topics from these interviews and co-design sessions were then mapped to topic areas within the domains of the READDY tool. Taken together, this revealed the most important topic areas that the KiT intervention would address and provide resources on. The interviews and co-design sessions also revealed additional topics that patients and providers felt were important but did not map to the READDY tool domains or topic areas. **See Appendix, Table 2: KiT**

Educational Topics and see Appendix, Table 3: KiT Intervention – Feature Category and Sample Dialogue; KiT Sample Messages in Appendix Page 37-40

Educational Content: We included only topics that were identified to be important to patients based on data from the interviews and co-design sessions and in the literature. We also only included topics for which there are credible resources available. Topics that will be relevant to all participants will be delivered to all participants as part of the “core educational curriculum” and topics that may not be relevant to all, will be delivered only to those who self-report low confidence or interest in those topics. The content of these messages will be developed by the research team and the tone and style of the messages will be developed by the eHealth innovation team with input from patients and providers in the co-design sessions.

Reminders: delivery of messages to help participants navigate diabetes care (e.g. reminders about booking appointments, refilling and paying for medication and supplies). See **Appendix, Table 3: KiT Intervention – Feature Category and Sample Dialogue, under section “Care Coordination”**; **KiT Sample Messages in Appendix Page 37-40**

Questionnaires and PREMs/PROMs: At baseline, a text message will be sent containing a URL linkout to a REDCap survey including the KiT survey (questionnaire about demographics and diabetes care and self-management) the READDY tool, SEDM, and BDA Stigma subscale. At 6 and 12-months after baseline, URLs will be sent via SMS to linkouts to REDCap surveys of the KiT survey (diabetes care and self-management) READDY tool, SEDM, and the BDA Stigma subscale. .

Other aspects of the KiT intervention messages: Participants in the intervention group will be sent messages at set intervals, however, they will have the option of increasing or decreasing the frequency of messages within a range of options and opt for messages to be sent on their preferred days of the week and time of day. Participants can also pause their messages at any time for a discrete period by texting the word “PAUSE”. The tone of the messages sent by the KiT intervention was developed by the eHealth innovation team and reviewed for acceptability with the help of our patient partner and adolescents who are of similar age to those who would be typically transitioning from pediatric to adult diabetes care.

KiT Intervention Technology and Development: the intervention algorithm will be built and managed by our third-party collaborator, Memotext, based in Toronto. Memotext is a digital patient engagement platform that uses health data and analytics to optimize digital communications. Memotext will be designing, developing, deploying and managing our study intervention in partnership with our study collaborators at UHN, the eHealth Innovation team. Memotext will work with SickKids REDCap administrators to ensure that REDCap API (Application Programming Interface) integration is enabled with SickKids REDCap servers in order to deploy chatbot link-outs to REDCap for PREMs and PROMs data collection. Memotext will only be receiving PHI in the form of participant phone number in order to enact registration between participant’s personal mobile devise (via SMS) and the chatbot; every participant will have their own Study ID number and Memotext will not be privy to the patients’ names or any other personal identifying information. During the consent process, participants will be made aware of all the information collected by the intervention, how this information will be used and who will have access to this information (Memotext and members of the research team); participants will be asked to provide their consent to collect this information within the KiT intervention during the e-consent process. Participants with any type of mobile device that is registered to any mobile network will be able to enroll in this study as text-messaging capabilities are universal for all mobile devices. Participants will be informed that only text-messages via SMS will be sent to their phones and will be advised to be connected to a wifi network when they are accessing links provided by KiT and when completing the outcome measures; this is to ensure that the participant does not incur extra out-of-pocket costs for data usage while not connected to a wifi network. Memotext’s system will maintain logs of all outgoing and

incoming messages, and this de-identified data (only linked to Study ID number), will be compiled into a feedback report that will be reviewed and evaluated by the research team on a periodic basis.

LLM Chatbot feature Technology and Development:

The LLM version of KiT is built using 3 components: 1) a web app with a prototype created with the Streamlit Python framework, which will provide the user interface; 2) an instance of AnythingLLM, an open-source application that turns documents into context that the LLM can use for reference during conversations; and 3) a Microsoft Azure OpenAI instance which runs the GPT-4 LLM.

The Streamlit app enables the user to send a query (Fig. 1). The app makes a call to the AnythingLLM API, sending the prompt to a workspace in the AnythingLLM instance. This instance is configured with the required documents that users need to chat with KiT. It is also connected to Microsoft Azure which is running the LLM. Azure returns the answer to the user query to AnythingLLM, which in turn returns the answer to the Streamlit app (Fig. 2).

A knowledge-base of diabetes-related documents comprised of the same resources used in the Q&A feature is used to create the LLM version of KiT. A research associate, research analyst and post-doctoral researcher at the Centre for Digital Therapeutics extracted the content from each resource to create the knowledge base. Each resulting document was then uploaded to AnythingLLM, which turns it into embeddings using OpenAI's text-embedding-ada-002 model (of note, these documents do not contain sensitive data; rather, they have information on diabetes-related topics freely available on the web). When a user makes a query, the embeddings are used by AnythingLLM to return the more relevant documents, which are then sent to the LLM running on Azure as context to create its answer. This minimizes the possibility of incorrect responses while ensuring answers are based on the curated knowledge-base. In addition, answers from the LLM also provide URL links to users (Fig. 1). If no relevant document is found by AnythingLLM, a standard reply is given: "There is no relevant information in this workspace to answer your query".

The Streamlit app and AnythingLLM instance will run on a server set up by MEMOTEXT. Users will be sent an URL to the Streamlit app as an SMS through MEMOTEXT, which will contain their study user ID as a parameter – for example <<https://llmbotlink.ca/?username=1>>. This username parameter in the URL (in this case representing study ID 1) is essential as it will allow us to log conversation history for each user.

Intervention arm: both intervention and control groups will continue with their usual diabetes care. In addition, the intervention group will receive the automated text messages for diabetes support and resources tailored according to their level of confidence and interest in transition topics, for 12 months. At baseline, individuals in the intervention group will receive a link via text-message that will take them to a questionnaire about their demographics and diabetes care and self-management, the READDY tool questionnaire, BDA Stigma Subscale, and SEDM on REDCap. Responses to the READDY tool will guide the personalized content of the educational text-messages. During the 12-month intervention period, participants in the intervention group will all receive messages to support participants to navigate diabetes care (e.g. reminders about upcoming appointments, refilling and paying for medication and supplies). At 6 and 12 months after enrollment in this study, all participants (intervention and control arms) will receive links via text messages that link-out to REDCap surveys for completion of: a questionnaire about diabetes care and self-management, SEDM, BDA Stigma subscale, and the READDY tool. Financial compensation will be provided for participant time to complete these outcome measures at baseline, 6, and 12 months.

Control arm: Participants randomized to the control arm will also be offered the same incentives to complete questionnaires (outcome measures) but will not receive any other components of the intervention – no personalized/customized support or diabetes resource messages and no reminders. Control arm participants will continue with their usual T1D transition care. They will be sent prompts via SMS asking them to complete the same questionnaire about diabetes appointments and care, PROMs/PREMs as the intervention group, at the same time-points of baseline, 6 months, and 12 months. The same financial incentive will be offered to both intervention and control groups to encourage participants to respond to these prompts.

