9 PARTICIPANT SAFETY

Due to the nature of the KiT intervention, we do not expect adverse or serious adverse events related to the intervention to occur. If a participant texts KiT any messages signalling a crisis situation (see table 4 for list of crisis key words that will be recognized by KiT), support messages will be delivered by KiT, encouraging the participant to reach out to medical professionals and will offer key contact information for appropriate assistance. The LLM chatbot also has instructions to send the same support messages in case any topic related to suicidal ideation is identified in the more natural language conversation. Participants will have the option to pause the KiT messages at any time if they feel that the intervention messages are causing them to feel uncomfortable or distressed until and if they feel ready to resume the messages again. Any elevated harm, discomfort or distress caused by the KiT messages, communicated to the research team by the participant, will be immediately reported to the Principal Investigator, and the Research Ethics Board, and entered the study database as a note to file.

English Safety Testing

We would like to use a new LLM (using GPT-4) chatbot feature to enhance the participant's experience for a more natural conversation. Prior to implementation, we will conduct a safety evaluation and are requesting access to the question data that enrolled participants have asked using the current question and answer feature. Please note, that the LLM chatbot feature will not be turned on until the English safety testing and analysis are completed. To do this safety evaluation, we will ask the patient questions (in addition to synthetically generated questions) to the KiT LLM and have human raters (investigators and

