patient partners) to score the answers from 1-5 based on accuracy, safety and a metric known as the global quality score. The validity and reliability of these metrics were established during several rounds of testing with the raters in addition to literature evidence. The LLM chatbot is not a learning model and will only utilize existing resources gathered for the KiT study. Although, since LLMs are stochastic in nature – i.e., may generate different answers to the same question at different times – we will ask each question 3 times. In addition, we want to test the use of LLMs as evaluators of the quality of answers. In order to do this, we will ask an LLM evaluator to also grade the answer to questions based on the aforementioned criteria, and compare this rating to the human raters. If successful, we plan to have the LLM evaluator continuously assess the questions asked by participants for any sensitive information (e.g., pertaining to suicidal ideation) and the quality of answers given, and flag any potentially harmful case for human review during the study.

It should also be noted we have previously assessed a prototype version of the KiT LLM and an LLM Evaluator (using GPT-4 accessed through UHN's Microsoft Azure subscription) on a set of synthetic questions, with promising results. We are in the process of improving these applications based on feedback from this initial assessment. Examples of these updates include stronger language on recommending visits to the emergency department in certain cases and explicit instructions to consider suicidal ideation when flagging potentially sensitive questions. We plan to test updated versions of the KiT and Evaluator LLMs with the questions already asked by participants during the study.

The English safety testing has been completed and the results are below. Once this amendment is approved them the LLM chatbot will be incorporated in Ontario sites.

English safety testing conclusions (please see accompanying PowerPoint presentation in CTO application)

Common questions to all raters (39 participant questions +12 synthetic questions)

- When considering the full set of questions (39 participant, 12 synthetic), the KiT LLM seems to perform well, with high scores in most metrics, particularly Safety.
- Overall the LLM Evaluator seems to act as, or more, conservative than most human raters (the exception being Patient Partner 2, which was slightly more conservative in general).

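### The protocol does not say that the chatbot's crisis response overrides its fixed no-match reply, which carries no crisis contact (minor, inexpensive safety improvement)

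*Protocol*

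**What the plan says.** Section 6.1.1 describes the chatbot's route in order. First comes retrieval: "When a user makes a query, the embeddings are used by AnythingLLM to return the more relevant documents". Those documents then go to the language model as context for its answer. For the case where nothing is retrieved, the section says "If no relevant document is found by AnythingLLM, a standard reply is given" and gives its text: "There is no relevant information in this workspace to answer your query". Item 5 of the feature list in the same section has the same rule without an exception: "If no resource relevant to the question is found, a message stating this is presented to participants".

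Section 9 covers crisis messages. For text messages the trigger is "If a participant texts KiT any messages signalling a crisis situation", with the keywords and standard response in Appendix Table 4. For the chatbot it says: "The LLM chatbot also has instructions to send the same support messages in case any topic related to suicidal ideation is identified".

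Section 9 also plans a human check. Chats on sensitive topics are flagged by the LLM evaluator, and the research team reviews them within 2-4 weeks of the flag to confirm that the bot gave the crisis contact. Unflagged chats can wait for an interim or end-of-study review. Before activation, raters score answers from 1 to 5 on accuracy, safety and global quality. The English test is complete. The French test is still to come, before the chatbot is switched on at the Quebec sites.

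**The concern.** A participant may type a message about suicide that resembles nothing in a library of diabetes resources. The rule in Section 9 calls for the support message. The rule in Section 6.1.1 calls for a bare statement that nothing relevant was found. The fallback is attached to the retrieval step, which is described before the language model answers. If the Section 9 instruction acts only within the model's answer, the fallback could come first.

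At stake is the reply that an at-risk adolescent sees at that moment. The Table 4 keyword trigger is described for texts, whereas the chatbot is reached by a link outside the SMS system. The sample Q&A messages in the Appendix also send participants to the chatbot when the SMS system does not recognise their question, so it will receive messages that the SMS tool could not match. The trial's estimates, power and error rates are not involved.

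**Working it through.** No statistical figure in the plan depends on this point, so the check compares the text and then works out the size of the extra testing.

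**The two rules side by side**

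| Question | No-match rule (Section 6.1.1) | Crisis rule (Section 9) |
|---|---|---|
| Trigger | Retrieval finds no relevant document | Suicidal ideation is identified in the chat |
| Reply | Fixed sentence of 12 words | Same support message as the SMS tool |
| Crisis contact in the reply | None | Yes (Table 4) |
| Relation to the other rule | Not stated | Not stated |

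A message can meet both triggers, and the visible text does not rank them.

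**What would reveal a wrong reply**

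1. *Before activation.* The tests use three 1-5 scores. A missing crisis contact could lower the safety score, but only if the question set holds a crisis prompt that matches no document. The synthetic questions may include one; the full set is not in this copy. The update on suicidal ideation named in Section 9 is "explicit instructions to consider suicidal ideation when flagging potentially sensitive questions", which concerns the flag. Another update in the same sentence, stronger language on emergency department visits, does concern replies, but not the no-match reply specifically.
2. *During the trial.* The one check described as confirming that the contact was given is the review of flagged chats: 2 × 7 = 14 to 4 × 7 = 28 days, counted from the flag.
3. *After the trial.* Section 8.5.3 looks at flagged and missed sensitive chats, to assess the evaluator.

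**Size of the proposed test**

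- English set, from Section 9: "Common questions to all raters (39 participant questions +12 synthetic questions", so 39 + 12 = 51 questions.
- Each question is to be asked 3 times: 51 × 3 = 153 answers.
- Assumed extra crisis prompts: 5, range 3 to 10.
- Extra answers per language: 5 × 3 = 15; range 3 × 3 = 9 to 10 × 3 = 30.
- Share of the English workload: 15/153 = 9.8%; range 9/153 = 5.9% to 30/153 = 19.6%.

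These percentages measure scoring effort and say nothing about how often a crisis message would get the wrong reply. The French set is assumed to be of similar size.

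**The case against.** The strongest reply is that Section 9 governs safety and already requires an automatic crisis message, with no condition about retrieval. Section 6.1.1 describes architecture, and a general fallback that does not restate a specific safety rule does not contradict it. That is a fair reading, and probably the intended one. It still leaves the order of the two steps unstated in the text.

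Several facts lower the exposure, and they stand:

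- Figure 2, the chat flow diagram, may already show the order, and the fuller English test report may already cover such prompts. Neither can be seen here, and their absence from this copy is no fault of the plan.
- Appendix Table 2 lists mental health among the topics, so many distress messages may match a document and never reach the fallback.
- The evaluator is planned to screen participants' questions as well as the answers, so a crisis question that met the fallback could still be flagged.
- The prototype screen in Figure 1 tells users to call 911 in an emergency and not to use the bot for urgent matters.

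A reader might infer that the chatbot has no crisis response. Section 9 states one. A reader might also infer from the 2-4 week interval that help to a participant is delayed by that long. It is not: the interval belongs to an audit of the bot, and the crisis response itself is meant to be automatic.

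A further objection concerns the remedy. Pasting the whole Table 4 message into the no-match reply would tell someone with an ordinary unanswered diabetes question that they seem to be having a difficult time. That objection is right, and the fix below avoids it.

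**Conclusion.** The point holds as a minor safety improvement. The protocol fixes a reply without a crisis contact and does not say that the crisis instruction takes precedence over it. The documents do not support calling this a contradiction or a demonstrated failure: no wrong reply is shown, no rate can be derived, and the processing order may be settled in a figure that is not visible.

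The case for acting is that the change covers the participant whatever the processing order proves to be, and that the French test, with its amendment, is still open. Confidence is medium, because it rests on the visible text alone. The 5 prompts (3 to 10) and the similar size of the French set are assumptions. Sample size, primary analysis and interpretation of the trial are unaffected.

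**What to change.** 1. In Section 6.1.1, both in item 5 of the feature list and in the chatbot technology text, state that the Section 9 crisis response overrides the no-match reply.
2. Add one neutral line to the no-match reply with 911 (911 or 811 in Quebec) and the crisis text line listed in Appendix Table 4. Leave out the opening sentence of the Table 4 message.
3. In the pending French safety test, include about 5 crisis prompts unlikely to match a diabetes document. Score each answer yes or no on whether the crisis contact was given.
4. Run the same prompts once in English, unless the full English report already covers them.

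The cost is one sentence in each of two places in the protocol, a slightly longer reply to ordinary unmatched questions, and about 15 extra answers to score per language (9 to 30).
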